2.2 Primary Endpoint

The primary endpoint for this study is wound healing (Group 2), as defined by the percent change in wound surface area (surface area is calculated in cm²) from baseline through the active treatment period. Specifically, wound care subjects will have the study device applied at baseline then re-applied two times per week for up to 4 weeks from the start of the active treatment period. Device reapplication will change to weekly when the principal or sub-investigator determines it is permissible or when a maximum of 4 weeks of treatment is reached. Device re-application will continue weekly until the wound is judged to be healed by the wound care practitioner or up to 3 months, whichever comes first. If after 2 consecutive months of treatment with the study device the wound does not exhibit healing, evidenced by a decrease in surface area (cm²), the subject will be returned to standard and established techniques of treatment consistent with the wound etiology.

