3.3 Expected Study Duration and Subject Participation

Group 1: The initial healthy volunteer safety study will last a total of 4.5 weeks. Healthy volunteers will wear the study device for 3 consecutive days (up to 72 hours), followed by weekly visits for 4 weeks of observation for tolerance, side effects, and/or adverse reactions.

For the purposes of this study, if 2 subjects experience an unacceptable adverse reaction warranting discontinuation of treatment in the opinion of the Investigators during the initial healthy volunteer phase, the study will be halted and Group 2 (and the remainder of the initial phase, if applicable) will not be completed. Allergic reactions and infections at the study device application site will be considered unacceptable at any clinical severity; other adverse reactions will be deemed "unacceptable" by the Investigators on a case-by-case basis dependent upon clinical severity (App. A).

Group 2: The wound care subjects will have twice per week study device applications to a specific ulceration for up to the first 4 weeks of treatment and then weekly reapplication thereafter. For subjects that exhibit any reduction in wound surface area, this application will occur until the wound is healed, or for up to 3 months (whichever occurs first). For subjects that do not exhibit any reduction in wound size at 2 months, application will stop and standard treatment protocols will be pursued. At the conclusion of the treatment window (up to 3 months), subjects will be followed every 3 months for 12 consecutive months for observation of late side effects or adverse reactions (3 months of active treatment, 12 months of follow-up observation, 15 months total).

IRB# 1331496 Page 19 Version 6.0

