5.0 STUDY PROCEDURES AND ASSESSMENTS

5.1 Schedule of Events

Group 1 (Healthy Volunteers):

The initial healthy volunteer safety study will last a total of 4.5 weeks. Healthy volunteers will have the study device applied for 3 consecutive days (up to 72 hours), followed by weekly visits for 4 weeks of observation for tolerance, side effects, and adverse reactions. Weekly visits will occur every 7 ± 2 days after the Day 3 visit.

Assessment	Screening (via phone)	Baseline	tion: Day 0Study Device	3 ± 0 days Treatment:	$y 7 \pm 2 \text{ days}^4 \text{ Follow-Up}$:	Unscheduled Visit
Informed Consent		X				
Medical history	X					
Concomitant medications	X	X	X	X	X	X
OhioHealth Research Institute Clinic Visit (Research Only)		X				
Critical Limb Care Center (Riverside Methodist Hospital Wound Center) visit (research-only)			X	X	X	
Shaving of left posterior calf		X				
Photograph			X	\mathbf{x}^5	X	
Noxsano Bandage application			X			
SAR Questionnaire			X	X	X	

Group 2 (Wound Care Subjects):

The wound care subject treatment period will consist of twice per week study device applications to a specific ulceration for up to the first 4 weeks of treatment and then weekly re-application thereafter. When deemed permissible by the clinical judgment of the principal or sub-investigator or when 4 weeks is reached, re-application of the study device will change to weekly. This weekly re-application will occur until the wound is healed, or for up to 12 weeks (whichever occurs first). For subjects that do not exhibit any reduction in wound size at 2 months, application will stop and standard treatment protocols will be pursued.

At the conclusion of the treatment period (maximum of 3 months), subjects will be followed every 3 months for 12 consecutive months for observation of late side effects or adverse reactions (up to 3 months of active treatment, 12 months of follow-up observation, 15 months maximum).

IRB# 1331496 Page 24 Version 6.0

⁴ Day 10, 17, 24, and 31

⁵ Photograph and compensation are given on Day 3 only during Treatment Period

Assessment	Screening / Baseline	Day OInitial Study Device	ery 3 ± 2 days ⁶ Treatment:	$2 \text{ try } 7 \pm 2 \text{ days}^7 \text{ Treatment:}$	$imo \pm 14 days^8 Follow-Up$:	Unscheduled Visit
Informed Consent	X					
Routine medical history / physical exam	X					X
Concomitant medications	X	X	X	X	X	X
HgbA1c (subjects with diabetes)	X					
ABI (subjects with arterial insufficiency)	X					

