- ♦ *Missed study follow-up visits:* Subjects who miss two consecutive follow-up visits will be contacted as described in section 5.12 in order to determine whether they wish to withdraw for the study or re-establish regular study follow-up visits. If subjects are able to re-establish study follow-up visits they may remain on the study. If the subject is unable to be contacted through the procedures outlined in section 5.12 data collection from the electronic medical record may continue, but the subject will be considered "lost to follow-up".
- ♦ Wound healing and discontinuation from study treatment: Clinical benefit may be determined during the treatment process by documentation of a healed ulceration, at which time the study device application will be discontinued. The post-treatment follow-up period will then begin for observation of late side effects and/or adverse reactions.
- ♦ *No evidence of wound healing at 2 months.* If a subject has no evidence of decreased wound surface area at 2 months (8 week treatment visit), the patient will be returned to standard and established techniques consistent with the wound etiology, and study follow-up will be discontinued.
- ♦ Wound < 50% healed at the completion of the study treatment period and discontinuation from study follow-up: If after 3 consecutive months (12 weeks) of treatment with the study device the wound does not exhibit at least a 50% decrease in surface area (cm²), the subject will be returned to standard and established techniques consistent with the wound etiology, and study follow-up will be discontinued. Clinical benefit experienced after the three-month treatment period, but not during the treatment period is not anticipated

In the absence of discontinuation due to adverse reactions (for both Groups 1 and 2) or wound healing outcomes (for Group 2 only) as indicated above, treatment may continue per the Schedule of Events (section 5.1) until one of the following criteria applies:

- ♦ Subject decision to withdraw from treatment (partial consent) or from the study (full consent),
- ♦ Death, or
- ♦ Funder reserves the right to temporarily suspend or prematurely discontinue this study.

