9.0 STATISTICAL CONSIDERATIONS

Primary Objective.

Group 1 (Safety): Healthy Volunteers. The initial phase of the study is designed to determine the safety of the study device in normal healthy volunteers without wounds. If there are no issues with tolerance, side effects, and/or adverse reactions in normal healthy volunteers, the second phase of the study will proceed with active wound care subjects.

Group 2 (Efficacy): Wound Care Subjects. The second phase of the study is designed to determine the effectiveness of the study device in wound healing in subjects with active wounds (see Primary Endpoint below), and to determine if the study device is equivalent to standard and established techniques (standard techniques demonstrate 50% wound healing at 2 months).

Primary Endpoint.

The primary endpoint for this study is wound healing (Group 2), as defined by the percent change in wound surface area (surface area is calculated in cm²) from baseline through the active treatment period. Wound care subjects will have the study device applied (and re-applied weekly) until the wound is judged to be healed by the wound care practitioner, for up to 3 months total duration. If after 2 consecutive months of treatment with the study device the wound does not exhibit at least 50% improvement in surface area (cm²), the subject will be returned to standard and established techniques consistent with the wound etiology. We will also determine if the study device is equivalent to standard and established techniques (standard techniques demonstrate 50% wound healing at 2 months).

Statistical Analysis Plan.

Descriptive statistics will comprise the bulk of the statistical analysis. Continuous variables will be reported as means and standard deviations, along with median and minimum/maximum values and compared between baseline and follow-up times using paired t-tests and/ or repeated measures ANOVA. Dichotomous and categorical variables will be reported as frequencies with percentages and compared between follow-up times using Chi-square tests or Kruskal Wallis tests. Imputation techniques will be used to account for missing data. Statistical significance will be set at p<0.05 for all the tests.

IRB# 1331496 Page 41 Version 6.0

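### Section 9.0 stops the device at 2 months below 50% improvement; Sections 3.3, 5.1 and 5.11 stop it only when there is no reduction

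*Combined protocol and SAP*

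**What the plan says.** Five sections state what happens to a Group 2 subject after 2 months on the device.

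- Section 9.0 (Primary Endpoint) sends the subject back to standard techniques on this condition: "If after 2 consecutive months of treatment with the study device the wound does not exhibit at least 50% improvement in surface area".
- Section 3.3 gives both branches. Continue: "For subjects that exhibit any reduction in wound surface area, this application will occur until the wound is healed, or for up to 3 months". Stop: "For subjects that do not exhibit any reduction in wound size at 2 months, application will stop and standard treatment protocols will be pursued".
- Section 5.1 repeats the stop branch: "For subjects that do not exhibit any reduction in wound size at 2 months, application will stop".
- Section 5.11 ties it to a visit: "If a subject has no evidence of decreased wound surface area at 2 months (8 week treatment visit"). It has a separate 50% criterion, applied at 12 weeks.
- Section 2.2 returns the subject to standard techniques if "the wound does not exhibit healing, evidenced by a decrease in surface area". Read naturally, this also means no decrease.

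Section 2.4 uses a 50% improvement within 2 months as well, but as the secondary endpoint (a proportion to be reported), not as a reason to stop the device.

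The same paragraph of Section 9.0 also describes the application schedule: "Wound care subjects will have the study device applied (and re-applied weekly) until the wound is judged to be healed". Section 2.2 instead has the device "re-applied two times per week for up to 4 weeks from the start of the active treatment period", then weekly. Sections 3.3, 5.1 (with its footnotes 6 and 7) and 5.8 agree with Section 2.2.

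**The concern.** One decision at one time point has two thresholds in the current text. They give opposite instructions for a wound that has shrunk, but by less than half.

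- **Treatment.** The conflict decides whether that subject stays on an investigational device. Section 8.7 bars deviations without prior written IRB approval except in medical emergencies, yet following either rule departs from the other.
- **Primary endpoint.** Percent change in area is taken from baseline over the active treatment period, so the stopping rule sets when that period ends. Section 9.0 also says missing data will be imputed. For such a subject, whether weeks 9 to 12 are missing or simply lie outside the period depends on which rule was followed.
- **Follow-up.** Section 5.11 ends study follow-up for no decrease at 8 weeks or for less than 50% at 12 weeks. Section 5.9 starts follow-up once the wound has healed or 3 months is reached. A subject stopped at week 8 under Section 9.0 with, say, a 25% reduction fits none of these descriptions.

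**Working it through.** The plan gives no figure to reproduce on this point. The check applies both rules to the same outcomes and then sizes the difference.

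**1. The two rules side by side (2-month decision, wound not healed)**

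| Reduction in area at 2 months | Section 9.0 | Sections 3.3, 5.1, 5.11 |
|---|---|---|
| −10% (wound larger) | stop | stop |
| 0% | stop | stop |
| 1% | stop | continue |
| 25% | stop | continue |
| 49.9% | stop | continue |
| 50% | continue | continue |
| 80% | continue | continue |

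The rules disagree exactly for reductions above 0% and below 50%.

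**2. Can the texts be read together?** Section 5.11 has one criterion at 8 weeks (no decrease) and another at 12 weeks (less than 50%). If Section 9.0 governed, nobody below 50% at week 8 would still be on the device, so the 12-week criterion could catch only subjects who reached 50% and then regressed. Nor is Section 9.0 just restating the secondary endpoint, because it attaches a change of treatment to the 50% figure.

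**3. Length of the active treatment period for a subject in the band**
- 2 months is the 8-week treatment visit (Section 5.11); maximum treatment is 12 weeks (Sections 5.1 and 5.11).
- Difference: 12 − 8 = up to 4 weeks. At one visit per week, that is up to 4 visits with an area measurement.

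**4. Re-application schedule, for a subject treated the full 12 weeks (Day 0 not counted, a change at week 12 counted)**
- Section 9.0: 12 × 1 = 12 changes.
- Footnotes 6 and 7 of Section 5.1: 4 × 2 + 8 × 1 = 16 changes.
- With k weeks of twice-weekly changes (k = 0 to 4): 12 + k, so the texts differ by 0 to 4 changes, depending on when the investigator permits weekly changes.

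**5. How many subjects could be in the band?** The documents give no distribution of healing at 2 months, so the share p is assumed to be 10% to 50% of those reaching week 8. Group 2 has 10 subjects (Section 3.2); the case of only 7 reaching week 8 is also an assumption.
- Expected number = n × p.
- Chance of at least one = 1 − (1 − p)^n.

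| n reaching week 8 | p | Expected number | Chance of at least one |
|---|---|---|---|
| 10 | 0.10 | 1 | 1 − 0.9^10 = 0.651 |
| 10 | 0.50 | 5 | 1 − 0.5^10 = 0.999 |
| 7 | 0.10 | 0.7 | 1 − 0.9^7 = 0.522 |
| 7 | 0.50 | 3.5 | 1 − 0.5^7 = 0.992 |

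These are chances that a subject falls in the band, not that a subject is handled wrongly.

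**The case against.** The best defence is that one sentence in Section 9.0 is the outlier. Section 5.11 is the discontinuation section; it lists its own criteria and otherwise lets treatment continue under Section 5.1, without referring to 9.0. Staff working from 5.1 and 5.11 would find a consistent rule. Section 2.2 also defines the primary endpoint and, on its natural reading, agrees with them. This lowers the risk of misapplication. It does not remove the conflict: Section 5.11 claims no precedence over Section 9.0, and 9.0 is where the analysis is specified.

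The effect on the analysis is also limited. Treatment length already varies between subjects, since healed wounds and wounds with no reduction stop early. Measurements up to week 8 are the same under both rules, so the 2-month secondary endpoint is largely unaffected, and the analysis is mainly descriptive. All of that stands. What remains exposed is the week 9 to 12 data of subjects in the band, and in a group of 10 each subject is 10% of the sample.

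The schedule mismatch is secondary. It may amount to no difference if weekly changes are permitted from the start, and a band subject stopped under Section 9.0 would have about 8 weekly changes, not 12. The wording still conflicts.

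**Conclusion.** The contradiction is real and is in current text. For any reduction above 0% and below 50% at 2 months, Section 9.0 stops the device and Sections 3.3, 5.1 and 5.11 continue it; Section 2.2 sides with the latter on its natural reading, though the finding does not depend on it. For each subject in the band, the documents support a difference of up to 4 of 12 weeks in the active treatment period over which the primary endpoint is measured. The number of such subjects is unknown; 1 to 5 of 10 rests on the assumed 10% to 50% share and on all 10 reaching week 8. Because the conflict determines who stays on the device and when the primary endpoint period ends, it must be corrected. The re-application wording is a smaller mismatch in the same paragraph.

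**What to change.** Reconcile Sections 2.2, 3.3, 5.1, 5.11 and 9.0 so that a single 2-month rule and a single re-application schedule appear throughout, and align the primary endpoint paragraph of Section 9.0 with them. Section 5.8 should be checked against the agreed schedule, and Sections 5.9 and 5.11 should make clear the follow-up status of anyone stopped at 2 months. Which rule and which schedule apply is for the investigators to decide; this review takes no position.

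The cost is a wording amendment with IRB approval. It adds no visits or measurements, and the primary endpoint itself is unchanged.

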1.3.4 Device Regulatory Pathway

[figure not shown]
Under 21 CFR 812.3(m), a significant risk device means an investigational device that:

- 1. Is intended as an implant and presents a potential for serious risk to the health, safety, or welfare of a subject,
- 2. Is purported or represented to be for use supporting or sustaining human life and presents a potential for serious risk to the health, safety, or welfare of a subject,
- 3. Is for a use of substantial importance in diagnosing, curing, mitigating, or treating disease, or otherwise preventing impairment of human health and presents a potential for serious risk to the health, safety, or welfare of a subject, and/or
- 4. Otherwise presents a potential for serious risk to the health, safety, or welfare of a subject.

The Noxsano Bandage is not an implantable device nor is it designed to sustain life; in this regard it is clearly not a significant risk device as defined by the FDA. The Noxsano Bandage also does not treat a disease, but does treat wounds which certainly could be considered an impairment of human health. The Bandage does not, in the manufacturer's opinion however, represent a serious risk to the health, safety, or welfare of the study subjects. The study subjects already have non-healing wounds that impair their health. The objective of the study will be to show improved healing relative to established techniques. Subjects will be monitored and returned to established techniques if the Noxsano Bandage fails to improve their healing. No preclinical evidence of significant risk has been demonstrated, and therefore significant risk is not anticipated or expected:

♦ NO is a naturally-occurring species produced by the body during healing as a biosignal, but is absent in chronic wounds.

IRB# 1331496 Page 15 Version 6.0

- ♦ Exogenous delivery replaces the missing NO at levels equivalent to those generated naturally, restoring the wound to its 'natural state.'
- ♦ NO is short lived (1-2 seconds) and therefore does not become systemic. Biological activity is limited to the wound.
- ♦ The level of NO is highly controlled by the electrochemical reaction, thus preventing any risk of overdose.
- ♦ The level delivered to the wound is fixed by the battery voltage and the formulation and cannot be altered by the patient.

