2.3 Secondary Objective (Group 2 only)

Group 2 (Efficacy): Wound Care Subjects. The secondary endpoint of the study is to determine if the study device is equivalent to standard and established techniques (standard techniques demonstrate 50% wound healing at 2 months) in subjects with active wounds.

[figure not shown]
IRB# 1331496 Page 17 Version 6.0

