2.4 Secondary Endpoint (Group 2 only)

Standard wound healing techniques generally demonstrate 50% wound healing at 2 months. Therefore, the secondary endpoint for this study is the proportion of wound care patients that have at least 50% improvement in surface area within 2 months of treatment. This information will be used to describe if the study device is equivalent to standard and established techniques.

IRB# 1331496 Page 18 Version 6.0

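### Section 9.0 undertakes to determine equivalence to standard care, but none of its planned analyses addresses it: wound area is tested only against baseline, and the responder proportion has no reference value

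*Combined protocol and SAP*

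**What the plan says.** **The aim.** Section 9.0 puts equivalence to standard techniques under the Group 2 primary objective and repeats it under the primary endpoint: "We will also determine if the study device is equivalent to standard and established techniques". The Objectives entry of the Protocol Summary agrees. Section 2.3 makes it the secondary objective: "The secondary endpoint of the study is to determine if the study device is equivalent to standard and established techniques". Section 2.4 is softer: "This information will be used to describe if the study device is equivalent to standard and established techniques". Section 1.3.4 words the aim differently again: "The objective of the study will be to show improved healing relative to established techniques".

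**The benchmark.** Section 2.4 states: "Standard wound healing techniques generally demonstrate 50% wound healing at 2 months". No source is cited. The secondary endpoint built on it is the proportion of patients with at least 50% improvement in surface area within 2 months.

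**The analysis.** The Statistical Analysis Plan paragraph of 9.0 calls the analysis mostly descriptive. Continuous variables are to be "compared between baseline and follow-up times using paired t-tests and/ or repeated measures ANOVA". Dichotomous and categorical variables are to be reported as frequencies with percentages and "compared between follow-up times using Chi-square tests or Kruskal Wallis tests". Significance is p<0.05 for every test. The paragraph contains no confidence interval, equivalence margin or reference value.

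**The design.** Group 2 is 10 subjects in a non-randomized study without a control arm (3.1, 3.2).

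**The concern.** A paired t-test or repeated measures ANOVA of wound area asks whether area changed over time. The equivalence aim asks how healing with the device compares with healing under standard care, which by the protocol's own figure is already substantial at 2 months. The first question can be answered yes whether the device is better than, the same as or worse than standard care.

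The one estimate that bears on the benchmark is the 2.4 proportion. The dichotomous rule would compare it between follow-up times, not with 50%, and gives it no interval.

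Followed exactly, then, the plan cannot answer an aim stated in the same section. What is at stake is interpretation: a significant fall from baseline could be reported as effectiveness or equivalence, and nothing in 9.0 says it may not be.

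**Working it through.** **Inputs.** From the documents: n = 10, one arm; alpha 0.05 (two-sided assumed, since 9.0 does not say); benchmark 50% at 2 months. The documents give no SD, effect size, margin or sample-size derivation, so there is no planned figure to reproduce. The SD of percent area reduction is assumed at 30, 40 or 50 points.

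**1. What a significant baseline test requires.** The smallest observed mean reduction giving p<0.05 is t(0.975, 9) × SD/√10 = 2.262 × SD/3.162:

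- SD 30: 21.5%
- SD 40: 28.6%
- SD 50: 35.8%

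All lie below 50%. The same figures are the half-widths of the 95% CI for the mean.

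**2. A single possible result.** Mean reduction 25%, SD 30: t = 25/(30/√10) = 25/9.487 = 2.635 on 9 df, p = 0.027. The 95% CI is 25 ± 2.262 × 9.487 = 25 ± 21.46, or 3.5% to 46.5%. The result is significant against zero and wholly below 50%.

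**3. Probability of significance if the device adds nothing, benchmark read as a mean reduction.** Simulation of 200,000 trials; remaining fraction of area gamma-distributed with mean 0.50, so that reduction cannot exceed 100%. The cm² rows use a paired t-test on area, with assumed baseline distributions below the 25 cm² limit.

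| Scale | SD 30 | SD 40 | SD 50 |
|---|---|---|---|
| Percent | 0.97 | 0.87 | 0.76 |
| cm², uniform 0.5 to 25 | 0.92 | 0.79 | 0.68 |
| cm², lognormal, median 4, log-SD 1 | 0.82 | 0.68 | 0.57 |
| cm², lognormal, median 2, log-SD 1.2 | 0.66 | 0.54 | 0.45 |

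A normal model on the percent scale (non-central t) gives 0.996, 0.94 and 0.80. With a true mean of 25%, half the benchmark, the percent-scale simulation gives 0.65, 0.48 and 0.39.

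**4. The same, benchmark read as half of patients reaching 50%.** Responders are uniform on 50% to 100% reduction. The answer then depends on the non-responders (negative values mean growth). Columns are percent, then cm² with the three baselines in the order above.

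| Non-responders' reduction | Percent | Uniform | Median 4 | Median 2 |
|---|---|---|---|---|
| 0 to 50% | 1.00 | 0.99 | 0.89 | 0.73 |
| −50 to 50% | 0.64 | 0.48 | 0.35 | 0.26 |
| −100 to 50% | 0.24 | 0.19 | 0.15 | 0.11 |

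**5. What the 2.4 proportion can show.** Exact (Clopper-Pearson) 95% CIs:

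- 2/10: 2.5% to 55.6%
- 5/10: 18.7% to 81.3%
- 8/10: 44.4% to 97.5%

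Every count from 2 to 8 has an interval containing 50%. If the true share is 50%, the count falls in that range with probability 1 − 2(1 + 10)/1024 = 0.979. If it is 25%, the probability is still 0.756.

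**6. Would a formal margin rescue the aim?** With a true mean reduction of 50% and an assumed margin of ±20 points, two one-sided tests (90% CI) declare equivalence with probability about 0.80, 0.28 and 0.07 at SDs of 20, 30 and 40.

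**The case against.** The strongest reply is that this is a first-in-human study of 10 patients, mainly descriptive by its own account. Section 2.4 already names the estimate that bears on the benchmark and promises only to describe. The primary endpoint is percent change from baseline, and a baseline test fits that literally. All of this stands, and it limits the harm. It does not remove the gap, because 9.0 and 2.3 still say *determine*, 9.0 sets significance for all tests, and even the descriptive comparison lacks an interval and a defined reference.

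A reader might infer more than the documents support:

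- *That 9.0 states a null of zero change, or makes p<0.05 the test of success.* It writes out no hypothesis; zero change is implied by the named tests. No success criterion is given. Nor is this inflated type I error: if wounds shrink, rejecting no change is correct but does not address the comparison.
- *That every aim is a comparison with standard care.* The Group 2 objective in 2.1 is effectiveness with no comparator named. The *improved healing* phrase stands in the regulatory-risk argument of 1.3.4, not in section 2.0, so it is an inconsistency of wording, not a separate formal aim.
- *That significance is likely whenever the device adds nothing.* This holds in 11 of the 12 cells under the mean reading but only 5 of 12 under the share reading (probability above 0.5), all on assumed distributions.
- *That 5.11 defines the benchmark.* Its criterion, a wound that "does not exhibit at least a 50% decrease in surface area", applies after 12 weeks of treatment to discontinuation. It does not say what standard care achieves at 2 months.
- *That a change from baseline means nothing here.* Section 1.3.4 describes the wounds as non-healing, so shrinkage has some descriptive value. Without a control it cannot be credited to the device over standard care.

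**Conclusion.** The concern holds in this form: 9.0 and 2.3 promise to determine equivalence to a 50% benchmark, and no test, interval or margin in 9.0 uses that benchmark. This rests on the text alone and needs no assumption about variability. It should be fixed.

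The size of the consequence does rest on assumptions. On the percent scale, a device that adds nothing reaches p<0.05 with probability about 0.76 to 0.97 if the benchmark is a mean reduction and the SD is 50 to 30 points. If the benchmark is a share of patients, the probability runs from about 0.1 to 1.0, depending on the non-responders and the scale. The worked result (25%, SD 30, p=0.027, interval wholly below 50%) shows that significance can coexist with healing below the benchmark. The harm is conditional on a baseline p-value being read as evidence for a comparative aim. The plan does not call for that reading, but does not exclude it.

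**What to change.** In 9.0, with matching wording in the Protocol Summary, 2.3 and 2.4:

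1. State that change-from-baseline p-values are descriptive and are not evidence of equivalence to standard care or of benefit over it.
2. Report the proportion with at least 50% area reduction within 2 months with an exact 95% CI, and the 2-month mean percent reduction with a 95% CI. Keep the existing primary endpoint through the treatment period alongside them.
3. Say whether the 50% benchmark is a mean area reduction or a share of patients, give its source, and set only the matching estimate against it.
4. Replace *determine* equivalence with *describe*, as 2.4 already has it; bring the *improved healing* wording in 1.3.4 into line; and state that an interval containing 50% does not show equivalence.

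The cost is a few sentences and one sourced definition. Endpoints, visits and sample size stay as they are, and the data are already collected. The downside is a weaker claim, wide intervals and a comparison that still rests on a historical figure. Keeping *determine* would instead need a justified margin and a sample size to support it.
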